12.1 Assessment of IMP/NIMP compliance

Noncompliance to the Protocol study procedures will be documented by the investigator and reported to the Sponsor as agreed. Persistent noncompliance may lead the patient to be withdrawn from the study. If a participant is 80% non-compliant as measured by the drug diary, then they will be withdrawn from treatment.

13. Monitoring

13.1 Study Monitoring

The sponsor will determine the appropriate level and nature of monitoring required for the trial. Risk will be assessed on an ongoing basis and adjustments made accordingly. The degree of monitoring will be proportionate to the objective, purpose, phase, design, size, complexity, blinding, endpoints and risks associated with the trial. A trial specific oversight and monitoring plan will be established for studies. The trial will be monitored in accordance with the agreed plan.

13.2 Recording of subject compliance information

A drug diary will be kept by the participant and completed on a daily basis for the duration of the study.

14. Discontinuation/withdrawal of participants

14.1 Protocol Treatment Discontinuation

In consenting to participate in the trial, participants are consenting to trial treatment, assessments, follow-up and data collection.

14.2 Discontinuation of Trial Treatment for clinical reasons

A participant may be withdrawn from trial treatment whenever continued participation is no longer in the participant's best interests, but the reasons for doing so must be recorded. Reasons for discontinuing treatment may include:

- 1 disease progression whilst on therapy
- 2 unacceptable toxicity (e.g. toxicity as listed in section 4 e.g. LFT >3x ULN)
- 3 intercurrent illness which prevents further treatment
- 4 patients withdrawing consent to further trial treatment (see section 14.3)
- 5 Any alterations in the participant's condition which justifies the discontinuation of treatment in the site investigator's opinion
- 6 Persistent non-compliance to protocol requirements
- 7 Patient unable to tolerate 40 mg Simvastatin

The decision to withdraw a participant from treatment must be recorded in the CRF and medical notes, and the sponsor when required should be notified in writing.

In these cases participants remain within the trial for the purposes of follow-up for safety and or data analysis according to the treatment option to which they have been allocated.

14.3 Participant withdrawal from trial treatment

In consenting to the trial, participants are consenting to trial treatments, trial follow-up and data collection. If a participant expresses their wish to withdraw from trial treatment, sites should explain the importance of remaining on trial follow-up and seek permission to allow use of routine follow-up data to be used for trial purposes. The importance of safety follow-up is explained in the participant in the Participant Information Sheet.

As participation in the trial is entirely voluntary, the participant may choose to discontinue trial treatment at any time without penalty or loss of benefits to which they would otherwise be entitled. Although not obliged to give a reason for discontinuing their trial treatment, a reasonable effort should be made to establish this reason, whilst remaining fully respectful of the participant's rights. If the participant gives a reason for their withdrawal, this should be recorded in the CRF and medical notes.

Participants who discontinue protocol treatment, for any of the above reasons, should remain in the trial for the purpose of follow-up and analysis.

If a participant is lost to follow-up at a site every effort should be made to contact the participant's GP to obtain information on the participant's status

14.4 Withdrawal of Consent to Data Collection

If a participant explicitly states they do not wish to contribute further data to the trial their decision must be respected and recorded in the CRF and medical notes.

14.5 Replacements

Participants who stop trial follow-up early will not be replaced.

14.6 Stopping rules

The trial may be stopped before completion for the following reasons:

On the recommendation of the Independent Data Monitoring Committee (IDMC)

On the recommendation of the sponsor and CI

If a participant is unable to tolerate Simvastatin at 40mg or 80mg dosage (see section 10.2).

14.7 Definition of End of Trial

- The expected duration of the trial is 2 years from recruitment of the first participant.
- The end of trial is defined as the date when sample analysis for Immune Parameters and Biomarkers has been completed.

15. Recording and reporting of adverse events and reactions

Collection, recording and reporting of adverse events (including serious and non-serious events and reactions) to the sponsor will be completed according to the sponsor's SOP (INV/S05).

15.1 Definitions

Table 1: Adverse Event Definitions

Adverse Event (AE)	Any untoward medical occurrence in a patient or clinical trial participant administered a medicinal product and which does not necessarily have a causal relationship with this treatment. Therefore an AE can be any unfavourable or unintended change in the structure (signs), function (symptoms) or chemistry (laboratory data) in a participant to who an IMP or procedural intervention has been administered, including occurrences which are not necessarily caused by or related to that product.
Adverse Reaction (AR)	Any untoward and unintended response in a participant to an investigational medicinal product which is related to any dose administered to that participant. This includes medication errors, uses outside of protocol (including misuse and abuse of product)
Serious Adverse Event (SAE), Serious Adverse Reaction (SAR) or Unexpected Serious Adverse Reaction	Any adverse event, adverse reaction or unexpected adverse reaction, respectively, that: 
 • results in death, • is life-threatening*, • requires hospitalisation or prolongation of existing hospitalisation**,

	
 • results in persistent or significant disability or incapacity, or • consists of a congenital anomaly or birth defect 
*A life- threatening event, this refers to an event in which the participant was at risk of death at the time of the event; it does not refer to an event which hypothetically might have caused death if it were more severe.
 
** Hospitalisation is defined as an in-patient admission, regardless of length of stay. Hospitalisation for pre-existing conditions, including elective procedures do not constitute an SAE."

	
*A life- threatening event, this refers to an event in which the participant was at risk of death at the time of the event; it does not refer to an event which hypothetically might have caused death if it were more severe.
 
** Hospitalisation is defined as an in-patient admission, regardless of length of stay. Hospitalisation for pre-existing conditions, including elective procedures do not constitute an SAE.

Unexpected Adverse Reaction (UAR)	
An adverse reaction the nature and severity of which is not consistent with the information about the medicinal product in question set out:
 
 (a) in the case of a product with a marketing authorization, in the summary of product characteristics for that product, (b) in the case of any other investigational medicinal product, in the investigator's brochure relating to the trial in question.
Suspected Unexpected Serious Adverse Reaction (SUSAR)	
 • An unexpected adverse reaction which is also categorised as serious.
Important Medical Event	
These events may jeopardise the participant or may require an intervention to prevent one of the above characteristics/consequences. Such events should also be considered 'serious'.

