			
7.5) will be excluded from the study. The patient information sheet will explain the risk of myopathy, explain to patients the need to inform doctors of the medications they take and advise patients on medications/supplements they need to avoid whilst on the study.
 
As a higher rate of myopathy has been observed in patients titrated to the 80 mg dose, Creatine Kinase (CK) will be tested at screening and monitored whilst on study. Patients who have a screening CK of $> 3 \times \text{ULN}$ will be excluded. If patients whilst on study have CK $> 3 \times \text{ULN}$ or present with clinical symptoms of myopathy, then, at the discretion of the treating clinician, simvastatin will be discontinued.

Simvastatin	Hyperglycaemia	Rare	
Some evidence suggests that statins as a class raises blood glucose and in some patients at risk of future diabetes. Patients who have or are at risk of Diabetes Mellitus will be monitored both clinically and biochemically according to national guidelines for Diabetes.

Simvastatin	Interstitial lung disease (dyspnoea, non productive cough)	Not Known	
If Interstitial lung disease is suspected whilst on the study, at the discretion of the treating clinician, simvastatin will be discontinued.

Simvastatin	Gastro-intestinal disorders (diarrhoea, nausea, vomiting, pancreatitis)	Rare	
Vital signs will be observed prior to study enrolment and at treatment visits to ensure significant hypotension or hypovolaemia does not occur during the trial. Patients will be advised to avoid dehydration and the volume status will be carefully monitored of the patients.
 
The Patient information sheet will explain this risk and advise patients on avoiding dehydration.

Simvastatin	Anaemia	Rare	Full blood Count will be tested at screening and monitored whilst on study. Patients whose results show clinical significant levels will be monitored and treated at the discretion of the treating clinician as per routine best medical practice.
Simvastatin	Elevated International Normalized Ratio (INR)	Very Rare	Very rare cases of elevated INR have been reported in patients taking oral coumarin anticoagulants. Patients who are on these anticoagulants will be monitored and treated at the discretion of the treating clinician as per routine best medical practice. Recommendations outlined in the SPC will also be considered.

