8.1.2 Trial participant exclusion criteria

Patients presenting with any of the following exclusion criteria (i.e. answers yes) at screening will not be eligible to proceed with the trial:

1. Unable to give informed consent.
2. Those that have experienced a relapse or have been treated with steroids (both i.v. and oral) for multiple sclerosis relapse within 3 months of the screening visit. These patients may undergo a further screening visit once the 3 month window has expired and may be included if no steroid treatment has been administered in the intervening period. Patients on steroids for another medical condition may enter as long as the steroid prescription is not for multiple sclerosis (relapse/progression).
3. Patient is already taking or is anticipated to be taking a statin or lomitapide for cholesterol control.
4. Any medications that unfavourably interact with statins as per Spc recommendations e.g.: fibrates, nicotinic acid, cyclosporin, azole anti-fungal preparations, macrolide antibiotics, protease inhibitors, nefazodone, verapamil, amiodarone, large amounts of grapefruit juice or alcohol abuse within 6 months.
5. The use of immunosuppressants (e.g. azathioprine, methotrexate, cyclosporin) or disease modifying treatments (avonex, rebif, betaferon, glatiramer, dimethyl fumarate, fingolimod) within the previous 6 months.
6. The use of mitoxantrone if treated within the last 12 months.
7. Patient has received treatment with alemtuzumab.
8. Use of other experimental disease modifying treatment (including research in an investigational medicinal product) within 6 months of baseline visit.
9. Active Hepatic disease or known severe renal failure (creatinine clearance <30ml/min).
10. Screening levels of alanine aminotransferase (ALT), aspartate aminotransferase (AST) or creatine kinase (CK) are three times the upper limit of normal patients.
11. If the patient reports any ophthalmic conditions such as glaucoma, ocular trauma or degenerative eye disease. . Cataracts are acceptable as long as they have not been advised to have surgery. No restrictions on post surgical care, unless the patient reports sight restricting capsule opacity.

12. Patient unable to tolerate or unsuitable to have baseline MRI scan (e.g. metal implants, heart pacemaker) or MRI scan not of adequate quality for analysis (e.g. too much movement artefact).
13. Females who are pregnant, planning pregnancy or breastfeeding.

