15.3.4 Seriousness

All events are assessed for seriousness as defined for an SAE in section 15.1.

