15.4.1 Flow Chart for SAE reporting

15.5 Serious Adverse Events which do not require immediate reporting

SPMS and PPMS are progressive neurological conditions and as such deterioration in neurological symptoms is expected. Symptoms of MS disease progression will be RECORDED in the participants' medical notes and in the CRF. However, SAE forms will not be completed and sent to the sponsor. The following SAEs are deemed as symptoms of MS disease progression and do not require immediate reporting:

- natural changes in motor, sensory, balance, sphincter (including urinary tract infections), visual, cognitive and fatigue levels

Symptoms of disease progression will be graded as follows:

Grade 1 relapse: relapse not treated with corticosteroids

Grade 2 relapse: relapse treated with corticosteroids, but not requiring hospitalisation

Grade 3 relapse: relapse treated with corticosteroids and requiring in-patient hospitalisation; or relapse not treated with corticosteroids but requiring in-patient hospitalisation

If the participant feels they are experiencing a relapse, they should contact their local MS team (nurse/consultant) or General Practitioner as per routine practice, so that appropriate management can occur. They should also inform the study team at their next scheduled visit, so that the relapse can be documented. At the Investigator's/nurse's discretion the patient can attend for an unscheduled visit, see section 9.3.4.

If the frequency or severity of these symptoms is not consistent with the SPC or disease the event must be reported to the sponsor as an SAE in the normal way

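### The hospitalisation footnote in Protocol 15.1 excludes every admission for a pre-existing condition, with no carve-out for unplanned worsening, and does not agree with 15.5

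*Protocol*

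**What the plan says.** Table 1 in Protocol 15.1 lists the criteria that make an adverse event, an adverse reaction or an unexpected adverse reaction serious. One criterion is that the event "requires hospitalisation or prolongation of existing hospitalisation". A footnote to that criterion adds "Hospitalisation is defined as an in-patient admission, regardless of length of stay" and then "Hospitalisation for pre-existing conditions, including elective procedures do not constitute an SAE". The footnote is printed twice. A separate row of the same table says that important medical events are also to be treated as serious.

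Section 15.3.4 refers every seriousness judgement back to this table: "All events are assessed for seriousness as defined for an SAE in section 15.1". Under 15.2, adverse events that are non-serious or MS-related go into source data only. Under 15.4, SAEs, SARs and SUSARs go into the medical records, the CRF and the SAE log, and (apart from the 15.5 exemptions) onto a form sent to the sponsor within 24 hours.

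The risk table in section 4 lists hyperglycaemia as a simvastatin risk and expects some participants to have diabetes already: "Patients who have or are at risk of Diabetes Mellitus will be monitored both clinically and biochemically according to national guidelines for Diabetes". Diabetes is not among the exclusion criteria in 8.1.2.

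Section 15.5 describes symptoms of MS progression as SAEs that need no immediate reporting. It has them recorded in the notes and the CRF, and includes in its Grade 3 a "relapse treated with corticosteroids and requiring in-patient hospitalisation". It also requires events whose frequency or severity does not fit the SPC or the disease to be reported to the sponsor as SAEs.

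**The concern.** An exclusion of this kind normally serves to keep planned admissions, which say nothing about the drug, out of the SAE record. The wording here is wider. It removes any admission for a condition the participant already had, whether planned or not and whether or not the condition has worsened. The Table 1 row it qualifies also defines serious adverse reactions and unexpected serious adverse reactions, so a judgement that the drug caused the worsening does not restore the event.

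What is at stake is the route that a drug-related admission takes. If it is classed as non-serious, the protocol gives it no SAE form, no SAE log entry and no CRF entry, and it cannot become a SUSAR. It would also be absent from any comparison of SAEs between the arms. Every participant has MS at entry, and some may have diabetes or other conditions, so the boundary between a pre-existing condition and a new event will come up in practice.

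**Working it through.** The point is one of definition. The plan gives no figure to reproduce, so the check sets the provisions side by side and follows a case through them.

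**Scope of the footnote (15.1).** The word "including" in "Hospitalisation for pre-existing conditions, including elective procedures do not constitute an SAE" puts elective procedures inside the excluded class without making them its boundary. There is no condition that the admission was planned before consent, and no exception for deterioration. None appears in 15.2 to 15.4 either. Section 15.5 has a safeguard, but only for MS symptoms.

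**Case A: a participant with diabetes at baseline has an unplanned admission for hyperglycaemia while on treatment, recovers, and the investigator judges the event possibly related.**

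1. Adverse event? Yes. The AE row covers any unfavourable change in signs, symptoms or chemistry.
2. Adverse reaction? Yes, on the investigator's causality judgement.
3. Serious through hospitalisation? It meets the criterion "requires hospitalisation or prolongation of existing hospitalisation", and any in-patient admission counts. The footnote then removes it, because diabetes was pre-existing.
4. Serious by another route? It is not fatal, life-threatening or disabling, and there is no congenital anomaly. The important-medical-event row remains, and that is a judgement.
5. If that judgement is not made, the event is non-serious. Section 15.2 puts it in source data only, and the CRF, SAE log and 24-hour form in 15.4 do not apply.
6. SUSAR? Table 1 requires a SUSAR to be categorised as serious, so the question of expectedness is not reached for that purpose. The provision in 15.4 that SARs and SUSARs are reported however late they occur does not help, since both terms depend on the same seriousness test.

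**Case B: a participant is admitted with an MS relapse.**

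| Question | 15.1 read literally | 15.2 | 15.5 |
|---|---|---|---|
| Is it an SAE on hospitalisation alone? | No, because MS is pre-existing | Not addressed | MS-progression events are called SAEs, exempt only from immediate reporting |
| Where is it recorded? | Not addressed | Source data only, as MS-related | Medical notes and CRF |
| If atypical for the SPC or disease? | Still excluded | Not addressed | Report to the sponsor as an SAE |

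Two conflicts follow. Sections 15.1 and 15.5 disagree on whether the event is an SAE, and 15.2 and 15.5 disagree on where it is recorded. The second conflict does not arise from the footnote, but it concerns the same events and should be settled in the same amendment.

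**The case against.** The strongest reply is that Table 1, read as a whole, already covers these cases. A worsening is itself an adverse event under the AE row, so an admission for it can be read as an admission for the new event and not for the stable condition. The important-medical-event row would catch many acute deteriorations, and fatal, life-threatening or disabling events stay serious regardless. This reading is reasonable and limits the scope: the gap exists only where hospitalisation is the sole criterion met and nobody applies the important-medical-event row. It does not close the gap. The footnote says outright that such admissions are not SAEs, while the alternative rests on inference or discretion. An investigator who follows the explicit sentence is following the protocol.

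On MS, the reply is that 15.5 is the specific rule and would in practice prevail. An ordinary MS admission gets no SAE form under either section, 15.5 provides for CRF recording, and atypical events have their own route to the sponsor. This stands, and it is why the practical effect of the 15.1/15.5 conflict is small.

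A reader might also infer several stronger points that the documents do not support:

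- **That only SAEs are assessed for causality and expectedness.** Section 15.3 requires both for every adverse event.
- **That nothing about such an event could reach the sponsor.** Section 15 refers the reporting of serious and non-serious events to a sponsor SOP that is not among the documents. What can be said is that the routes written in the protocol are bypassed.
- **That renal disease is a further example.** Section 8.1.2 excludes "Active Hepatic disease or known severe renal failure (creatinine clearance <30ml/min", which might suggest that milder impairment is admitted. But section 4 adds exclusions for known renal failure and for laboratory limits, and it describes acute renal failure as secondary to rhabdomyolysis. That would be a new event, which the footnote does not remove.
- **That a particular number of serious events would be missed.** The documents give no event rate and no frequency of comorbidity.

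**Conclusion.** The concern holds within limits. As written, an unplanned admission for worsening of a pre-existing condition is non-serious when hospitalisation is the only criterion met and the event is not judged an important medical event. It then stays in source data and bypasses the SAE log, the CRF, the 24-hour form and possible SUSAR classification, even when judged related to the drug. Pre-existing diabetes is the clearest example, because section 4 both expects it and lists hyperglycaemia as a risk.

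Sections 15.1 and 15.5 also classify MS admissions differently, and 15.2 and 15.5 differ on where MS events are recorded. These are real inconsistencies with little practical effect.

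The number of affected events in this 40-patient trial is unknown. The conclusion assumes that investigators apply the footnote as it is worded and that the SOP, which is not available here, does not override it. If the footnote was meant only for planned admissions, the amendment simply states that intent. The change should be made, because the defect concerns safety reporting and is easy to correct.

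**What to change.** Reword the footnote in 15.1, in both places, so that it excludes only admissions that were planned before consent, or are elective, for a condition that has not worsened since baseline. Add that an unplanned admission, including one for worsening of a pre-existing condition, meets the hospitalisation criterion, with MS events then handled under 15.5.

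Align 15.1, 15.2 and 15.5 on two points: whether an admission for MS is an SAE exempt only from immediate reporting, and whether MS events are recorded in the CRF or in source data only.

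The cost is one duplicated footnote and consequential wording in two other sections. The downside is a few more SAE forms.

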15.2 Recording adverse events

All adverse events following IMP administration will be recorded in the medical records in the first instance. As simvastatin is a licensed product with a well-established safety profile, AEs that are non-serious or MS related (see section 15.5 for MS expected adverse events) will be recorded in the source data (Medical records and Participant diary cards) only.

All adverse events will be recorded with clinical symptoms and accompanied with a simple, brief description of the event, including dates as appropriate.

Clinically significant abnormalities in the results of objective tests (e.g. laboratory variables) will also be recorded as adverse events in the medical notes and if assessed as serious they will also be recorded on the SAE log and in the CRF. If these events are not expected as part of disease or IMP, these will be recorded as unexpected.

All adverse events will be recorded until 6 weeks after the participant's final clinical visit (EOS).

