Venepuncture for Blood Tests	Risk of discomfort, bruising, excessive bleeding, fainting or feeling lightheaded, hematoma & infection	Venepuncture risks will be managed using standard clinical care precautions which include wearing protective clothing, hand and surface hygiene. Risks to participants from venepuncture will be managed using standard clinical care. Non clinical staff performing venepuncture will receive appropriate training. Every effort will be made to make participants feel comfortable before, during and after venepuncture by encouraging participants to relax and talking

		
through any concerns they have about the procedure.
 
Trust incident reporting will apply and be followed in the event of patient/staff needle stick injury.

MRI	
MRI is generally well tolerated. There can occasionally be some discomfort and/ or claustrophobia. It is however unsafe in patients who have metal implants or heart pacemaker. Also not recommended in patients who are pregnant.
	
Trial participants will have had MRI as part of the diagnostic pathway and will be familiar with it. During the scan they have real-time contact with the radiographer with any concerns and can halt the scan if needed. Patients fitted with pacemakers or permanent hearing aids are excluded because these are metal containing products and highly unsafe for MRI. Protocol excludes patients who are unable to tolerate scans. Pregnant participants will be excluded from the study and women of child bearing potential will need to have a negative urine pregnancy test.

Advanced retinal imaging inc. OCT	
Patients may have some discomfort from glare induced by having their eyes dilated. There is also a small risk of eye irritation from application of the drops.
	
Light levels are well below recommended levels and are electronically controlled to prevent accidental over exposure. Patient will be advised to bring sunglasses to protect against glare. Lights within the building are designed to account for increased light sensitivity. Irritation from the drops is mitigated by use of a sterile single use applicators.

In accordance with the MRC/DH/MHRA Joint Project Risk-adapted Approaches to the Management of Clinical Trials of Investigational Medicinal Products, this trial is categorised as:

Type B = somewhat higher than the risk of standard medical care

5. Objectives

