15.3 Assessment of Adverse Events

Each adverse event will be assessed for severity, causality, seriousness and expectedness as described below.

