15.4 Procedures for recording and reporting Serious Adverse Events

All serious adverse events (SAEs/SARs/SUSARs) will be recorded in the medical records and the CRF, and the sponsor's SAE log. The SAE log of SAEs will be reported to the sponsor at least once or twice per year in liaison with JRO Pharmacovigilance Manager.

All SAEs will be recorded from the time of the first enrolled participant's drug release (at Visit 2) until 6 weeks post-treatment (defined as six weeks beyond end of treatment).

All SAEs (except those specified in section 15.5 as not requiring reporting to the Sponsor), must be recorded on a serious adverse event (SAE) form. The CI/PI or designated individual will complete the sponsor's SAE form and email the form to the Sponsor at [contact] within 24 hours of his / her becoming aware of the event. The Chief or Principal Investigator will respond to any SAE queries raised by the sponsor as soon as possible.

Completed SAE forms must be sent within 24 hours of becoming aware of the event to the Sponsor
Email forms to [contact]

[figure not shown]
Reporting to the sponsor will be completed as per the sponsor's SOP and using the UCL SAE form (INV/S05) as amended for the trial.

SAE's will be reported to the sponsor until the end of the trial. SAR and SUSAR will need to be reported to the Sponsor irrespective of how long after IMP administration the reaction has occurred.

Participants must be followed up until clinical recovery is complete and laboratory results have returned to normal or baseline values, or until the event has stabilised. Follow-up should continue after completion of protocol treatment and/or trial follow-up if necessary.

Follow-up SAE forms (clearly marked as follow-up) should be completed and emailed to the JRO as further information becomes available.

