23.2 Statistical Analysis Plan

The stats analysis plan will be produced well in advance of seeing the data. It will specify both the primary analysis (in detail) and the secondary analyses (in less detail), including details of the analysis methods and any pre-specified covariates for adjustment such as the minimisation variables. It will also provide details of adverse events analyses and per-protocol analysis using adherence information. The analysis plan will describe contingency analysis should the assumptions of the primary methods not be satisfied by the data. A CONSORT flow diagram will be produced.

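### Non-serious adverse events stay in source records and the SAP has no adverse event analysis, so a comparison of them by arm has neither CRF data nor a plan behind it

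*Protocol*

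**What the plan says.** **Recording.** Protocol 15.2 cites the drug's licence and known safety profile, and then says that events that are non-serious or related to MS "will be recorded in the source data (Medical records and Participant diary cards) only". For clinically significant laboratory abnormalities it adds that "if assessed as serious they will also be recorded on the SAE log and in the CRF". Serious events are handled differently in 15.4: "All serious adverse events (SAEs/SARs/SUSARs) will be recorded in the medical records and the CRF, and the sponsor's SAE log".

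**Database.** Section 20.2 makes an Excel file the electronic CRF. It allows for a class of data held only in source, and gives diary cards as an example.

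**Assessment.** Section 15.3 states: "Each adverse event will be assessed for severity, causality, seriousness and expectedness as described below". Section 15.3.2 describes causality as a judgement made when the CRF is completed.

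**Analysis.** Of the SAP, section 23.2 says: "It will also provide details of adverse events analyses". Section 2 of the SAP covers the primary, secondary, exploratory and sensitivity analyses, model checks and the absence of an interim analysis. It has no safety or adverse event analysis and names no source of adverse event data.

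**The concern.** Non-serious events are elicited, described, dated and graded in both arms, but the stated rule then keeps them out of the database used for analysis. The analysis announced in 23.2 is missing from the SAP, and if it were added now it would have only serious events to work on.

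What drops out is what usually describes tolerability. In 15.3.1, grade 3 is the first grade to mention hospitalisation, and hospitalisation is one of the seriousness criteria in 15.1. Most grade 1 and 2 events would therefore not be serious. Section 10.2 changes the dose on the basis of intolerance, which need not be serious either, and nothing requires the event behind such a change to be entered in the CRF.

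Section 4 notes a higher rate of myopathy in patients titrated to 80 mg, and 3.3 says the drug is used outside its posology. A placebo-controlled comparison at this dose is useful to later trials, and it would be lost for want of transcription.

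**Working it through.** The plan gives no figure on this point, so the main check sets the sections side by side.

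| Item | Where it is recorded | Section | Comparable by arm as written? |
|---|---|---|---|
| Serious adverse events | Notes, CRF, SAE log | 15.4 | Yes |
| Non-serious adverse events | Notes and diary cards only | 15.2 | No, unless abstracted |
| MS-related events | Source only in 15.2; notes and CRF in 15.5 | 15.2, 15.5 | Sections conflict |
| Laboratory abnormality logged as an AE | CRF only if serious | 15.2 | Only if serious |
| CK and alanine transferase values | Safety bloods at Visits 1 to 4 | 11.1, Appendix 1 | Yes, if results are transcribed as 20.2 implies |
| Decision to withdraw treatment | CRF and notes; reasons must be recorded | 14.2 | Yes |
| Participant's own reason for stopping, if given | CRF and notes | 14.3 | Yes |
| Drug administration | Source and CRF | 7.5 | Yes |
| Event behind a dose reduction or a stay on 40 mg | No CRF entry named | 10.2 | No |

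Three inconsistencies follow.

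1. Section 15.2 keeps MS-related events out of the CRF, while 15.5 puts MS progression symptoms in it.
2. Section 15.3.2 has causality judged at CRF completion, but most events have no CRF entry.
3. Section 23.2 announces adverse event analyses, and the SAP has none.

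**What 20 per arm could show.** The documents give no event rates, so the rates below are assumptions.

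- Chance of at least one event among 20 patients, 1 − (1 − p)^20: 33% at p = 2%, 64% at 5%, 88% at 10%.
- Power for two proportions, two-sided 5%, normal approximation: Φ{[√n·|p1 − p2| − 1.96·√(2·p̄·(1 − p̄))] / √(p1(1 − p1) + p2(1 − p2))}, with n = 20 and p̄ the mean of the two rates.
  - 10% v 30%: (0.894 − 1.109)/0.548 = −0.39, power about 35%.
  - 10% v 50%: (1.789 − 1.270)/0.583 = 0.89, power about 81%.

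Rare events would yield little information in either arm. Common events could show a difference only if it were large. The case for capturing them is therefore description, not hypothesis testing.

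**Size of the task.** Appendix 1 schedules adverse event recording at Visits 2, 3 and 4. For 40 patients that is 40 × 3 = 120 scheduled patient-visits, plus unscheduled visits, telephone contacts and the six weeks after the final visit that 15.2 covers.

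**The case against.** The strongest reply is that this is a reasoned choice. Section 15.2 gives its rationale, 20.2 expressly allows source-only data, and section 3.3 says the earlier phase II trial found doses up to 80 mg/day safe. The trial studies mechanism, and no objective in sections 5.3 to 5.6 is safety or tolerability. Section 4 rates the trial as "Type B = somewhat higher than the risk of standard medical care", but nothing in the documents links that rating to what must enter the CRF. Section 23.2 also does not say that non-serious events will be analysed. All of this stands, and it limits the weight of the point.

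A reader might go further and infer that tolerability cannot be compared between arms at all. The documents do not support that. Withdrawals and doses taken reach the CRF, and section 15.1 treats important medical events as serious, so those reach it too. Non-serious events exist in source, dated and assessed, for both blinded arms and could be abstracted.

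A reader might also infer that muscle and liver enzyme rises are lost. They are not: CK and alanine transferase are measured at each scheduled clinic visit. Section 15.2 decides only whether an abnormal result is also entered in the CRF as an adverse event.

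The reply does not explain why sections 15.2, 15.3.2 and 15.5 disagree, or why the SAP omits what 23.2 says it will contain.

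**Conclusion.** The point holds in a limited form. Followed as written, the plan gives a between-arm comparison of non-serious adverse events no CRF data and no analysis. What can be compared is serious events, withdrawals and their recorded reasons, drug administration and scheduled laboratory values. The reason for a dose reduction or a stay on 40 mg has no explicit place in the CRF.

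This assumes that "only" in 15.2 means what it says, that no abstraction step exists in a document outside the protocol and SAP, and that laboratory results are transcribed as 20.2 suggests. The primary cerebral blood flow result is not affected. This is a cheap improvement to the safety reporting, not a flaw in the trial's main inference.

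**What to change.** 1. Enter all adverse events in the CRF and its Excel database: term, dates, grade, causality, seriousness, dose at onset and action taken on study drug. If the CRF can no longer be changed, abstract the same items from source for both arms, under blind and before database lock. Abstraction after unblinding would risk bias.
2. Add a descriptive safety section to the SAP, by arm: patients with at least one event and number of events by type and grade; serious events; dose reductions and withdrawals with reasons; and CK and alanine transferase values by visit. Given the numbers, present counts and proportions without significance tests.
3. Reconcile 15.2 with 15.3.2 on where causality is recorded, and with 15.5 on whether MS-related events enter the CRF.

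The cost is one CRF page, modest data entry for 40 patients, and a short addition to the SAP. The events are already being elicited and assessed, so patients face no extra procedures.
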